Approximately 7 days after the last retrieval-extinction session, we will test participants' responses to alcohol cues using two Pavlovian procedures, renewal and reinstatement, that have previously been used in studies of laboratory animals to differentiate the effects of retrieval-extinction from extinction alone (Luo et al., 2015). At this visit, participants will return their smartphones.

Each participant will receive a follow-up phone call approximately 30 days after his or her last visit.

The study will take each participant approximately 3 months to complete, depending on how close together sessions can be scheduled. Each type of session is described in more detail in the Study Procedures section.

2. Study procedures

Study Timeline

Session	Beverage	Empty Packaging	Cue Script	Drinking
2-5. Retrieval	X	X	-	X
2-5. Extinction	X	X	X	-
6. Renewal, same room	X	X	X	-
6. Renewal, different room	X	X	X	-
6. Reinstatement, same room	X	-	-	X

Experimental groups and randomization

As we mentioned above, we needed to limit the number of groups for practical reasons. Participants will be randomized to one of three groups: (1) alcohol retrieval / alcohol extinction, (2) soft-drink retrieval / alcohol extinction, and (3) alcohol retrieval / soft-drink extinction. The use of these two control groups (groups 2 and 3) assesses whether the retrieval-extinction procedure requires both its retrieval component and its extinction component. Group 2 represents a traditional CET approach, with

Abbreviated Title: Lab/GMA drinking

Version Date: 2/16/2022

no relevant retrieval procedure. Group 3 controls for mere alcohol exposure in the laboratory, which has actually been shown to have some effect on subsequent drinking (Hodgson & Rankin, 1976; Modell et al., 1993; Pratt & Davidson, 2005).

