Finally, participants will be asked to relax in a third, neutral room of the laboratory where their BAC will be checked every 20 minutes until $\leq .01\%$. Participants may be released from the laboratory when their Pre-discharge sobriety test is within normal limits and their BAC is $\leq .01\%$. A copy of the sobriety test is included in the Appendix.

Our decision to use four separate extinction sessions was based on data from previous studies, which showed that by the fourth session of extinction, craving for alcohol had decreased either to the point of not being different from that of neutral-beverage control participants, or by $> 50\%$, or by reaching an asymptote such that additional sessions produced no further consistent declines craving (Blakey & Baker, 1980; Staiger & White, 1991; Staiger et al., 1999; MacKillop & Lisman, 2008). It is possible that US exposure (alcohol drinking for memory retrieval) will itself facilitate extinction (Luo et al., 2015). We believe that it is important to attempt to conduct a sufficient number of extinction sessions to allow the soft-drink retrieval / alcohol extinction group, as well as the alcohol retrieval / alcohol extinction group, to achieve a significant attenuation of cue effects.

c. Session 6: Post-treatment effects of cues in the laboratory

Participants will return their smartphones at the beginning of this visit. They will also complete a timeline follow-back calendar (Sobell et al., 1979; Sobell et al., 1996a) covering the time between Session 5 and Session 6 to provide a retrospective report of “post-extinction” drinking for comparison with that week’s GMA reports.

In the session, all participants will be presented with alcohol cues and an alcohol-containing beverage (i.e., regardless of their previous group assignment to receive only a soft drink or soft-drink cues). Cue-induced craving and physiological changes will be measured in response to two procedures known to enhance responding after Pavlovian extinction procedures (Todd et al., 2014) and to differentiate the effects of extinction with or without prior memory retrieval in laboratory animals (Luo et al., 2015): (1) a renewal procedure, in which the extinguished response may reappear because the CS is presented in a new context and (2) a reinstatement procedure, in which the extinguished response may

Abbreviated Title: Lab/GMA drinking

Version Date: 2/16/2022

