Stored biological specimens will be kept in a secure freezer in the Archway's NIDA freezer room until they are analyzed (BRC building; room 01B405). Specimens that are not used up in the analyses will be saved, but will not be used for any purpose not described in the protocol without prior IRB approval.

Urine samples will be kept in a secure freezer in the Archway's NIDA freezer room until they are analyzed (BRC building; room 01B405) and tracked by barcode. Those that are not used up in the analyses will be disposed of after the study. They will not be used for any purpose not described in the protocol without prior IRB approval. Any unplanned loss or destruction of the samples will be reported by the PI to the IRB.

I. Statistical Analysis

1. Outcome measures

Primary: (1) self-reported alcohol craving during the laboratory sessions, (2) GMA reports of alcohol craving and drinking.

Secondary: (1) self-reported alcohol craving and drinking at the 30-day follow-up, (2) heart rate during laboratory sessions and GMA collection periods, and (3) biomarkers for drinking, detected in urine samples collected during laboratory sessions.

2. Analysis of study outcomes

There are two ways in which we are performing multiple tests of statistical significance. First, we have two co-primary outcomes: a lab measure and an ambulatory measure. This design is actually conservative, because we will not consider US retrieval-extinction fully successful if it affects only the first outcome (protection from renewal/reinstatement in a lab setting) without affecting the second outcome (changes in daily-life behavior).

Second, we need to compare our experimental group to each of the two control groups—we expect the control groups to be similar to each other. If the experimental group differs from only one of the control groups, we will have to conclude that the effect of US retrieval-extinction did not actually require both retrieval and extinction, and thus worked via some unexpected mechanism. Although we might ultimately need to perform the two comparisons separately to explore unexpected findings, our main planned analysis is a single test of the joint hypothesis that the experimental group differs simultaneously from both control groups.

Our specific tests will be as follows.

Abbreviated Title: *Lab/GMA drinking*

Version Date: 2/16/2022

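### Beating both controls shows that each component adds to the other; without a soft-drink/soft-drink group it cannot show that retrieval and extinction interact

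*Combined protocol and SAP*

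**What the plan says.** Section E.2 (Experimental groups and randomization) assigns participants to "1) alcohol retrieval / alcohol extinction, (2) soft-drink retrieval / alcohol extinction, and (3) alcohol retrieval / soft-drink extinction". Below these are E (experimental), A and B. The section says that using the two controls "assesses whether the retrieval-extinction procedure requires both its retrieval component and its extinction component". It describes A as conventional cue exposure and says of B: "Group 3 controls for mere alcohol exposure in the laboratory, which has actually been shown to have some effect on subsequent drinking".

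Section E.2.b explains the choice of four sessions partly by the wish for group A, too, "to achieve a significant attenuation of cue effects".

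Section I.2 plans "a single test of the joint hypothesis that the experimental group differs simultaneously from both control groups", and adds that "we expect the control groups to be similar to each other". If E differs from only one control, the stated conclusion is that the effect "did not actually require both retrieval and extinction, and thus worked via some unexpected mechanism". The section does not say in words what a difference from both controls would establish.

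The Précis names the mechanism in view, reconsolidation: a freshly retrieved association is easier for extinction to disrupt. The table in Section C lists extinction alone as giving no protection against renewal or reinstatement, which are the two scores of co-primary outcome 1.

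**The concern.** The three groups are three cells of a 2x2 layout, retrieval beverage by extinction cue. The reconsolidation account is a statement about interaction: retrieval matters because it changes what extinction does. Neither planned contrast measures that. E against A gives the effect of alcohol retrieval when alcohol extinction is present. E against B gives the effect of alcohol extinction when alcohol retrieval is present. Both can be favourable with no interaction at all, if each component has a modest benefit of its own.

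At stake is the explanation attached to a positive trial. It could be credited to the retrieval-extinction combination when ordinary cue exposure plus laboratory drinking would fit the same data. This matters most for the GMA outcome, which Section D treats as sufficient evidence of efficacy on its own. The documents nowhere mention additive effects or limit the mechanistic reading.

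**Working it through.** **Inputs.** From Section J: 75 evaluable participants, 25 per group, two-sided alpha 0.05, f² = 0.13, stated d = 0.61, one baseline covariate. From Section I.2: a joint Wald test with E as the reference group. The documents give no size for either component alone, so the sizes below are assumptions, shown at two values.

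**1. The plan's own figure.** The R²-increase test has 2 tested and 3 total predictors, so df = 2 and 75 − 3 − 1 = 71, with noncentrality 0.13 × 75 = 9.75. Power is 0.787, which agrees with the stated 0.80 to within two points.

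**2. Scale.** If E differs from two equal controls by δ residual SD, f² = 2δ²/9, so f² = 0.13 gives δ = √(0.13 × 9/2) = 0.765. Section J gives d = 0.61. I use both as the range; nothing below turns on which is correct.

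**3. Algebra.** Lower is better. Let C be the unobserved soft-drink/soft-drink mean, r and x the benefits of retrieval and extinction alone, and s the extra benefit of combining them.

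- E = C − r − x − s; A = C − x; B = C − r
- E − A = −(r + s); E − B = −(x + s); A − B = r − x
- Interaction: E − A − B + C = −s, which requires C

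Similar controls do not settle the matter. A = B says only that r = x, not that both are zero.

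**4. Two opposite truths.** The planned regression was simulated with 25 per group and 8,000 runs per scenario.

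| | Pure synergy (r = x = 0, s = δ) | Pure additivity (r = x = δ, s = 0) |
|---|---|---|
| E − A and E − B | −δ and −δ | −δ and −δ |
| A − B | 0 | 0 |
| True interaction | −δ | 0 |
| Joint test significant, δ = 0.765 | 0.77 | 0.78 |
| E significantly better than both, δ = 0.765 | 0.62 | 0.63 |
| Joint test significant, δ = 0.61 | 0.58 | 0.57 |
| E significantly better than both, δ = 0.61 | 0.40 | 0.40 |

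The columns differ only by simulation error. For a proportion p = 0.63 over 8,000 runs, the standard error √(p × (1 − p) ÷ runs) is 0.005.

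**5. Why both pairwise contrasts are needed.** With r = 0.765 and x = s = 0, E beats A but equals B. The joint test is still significant in 78% of runs, while E is significantly better than both in 3%. The joint test alone therefore does not show that E beat both.

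**6. What a fourth group would need.** The interaction has standard error SD × √(4/n per cell). With 25 per cell (100 evaluable), power is 0.33 for an interaction of 0.61 SD and 0.48 for 0.765 SD. Power of 80% needs n = 4 × (2.80/δ)² per cell, where 2.80 is the sum of the normal quantiles for two-sided alpha 0.05 and 80% power: 85 (340 evaluable) at 0.61 SD, or 54 (216 evaluable) at 0.765 SD.

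**The case against.** The strongest reply is that the trial is a dismantling design. In that ordinary sense, beating both controls does answer the question, because taking away either component loses benefit. This stands, and the proposed wording keeps it. It does not reach the reconsolidation mechanism.

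Second, a reader might infer that Section I.2 declares beating both controls to be proof of that mechanism. It does not. It states only the refuting direction: differing from one control alone counts against the need for both. That rule is sound, subject to power. The positive reading comes from Section E.2's statement of what the controls assess, and from I.2's contrast with an unexpected mechanism.

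Third, a reader might infer that the protocol itself expects two additive benefits. The documents do not support this. Section E.2 reports an effect of laboratory alcohol without its direction. Section E.2.b aims at attenuated cue effects, not at either co-primary outcome as analysed. Section C calls standard extinction dependent on place, time and drug-free state, and reports mixed results for cue-exposure therapy. The rival is left open, not predicted.

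Fourth, the additive model fits co-primary outcome 1 poorly. Its scores are within-session differences, so a uniform fall in craving cancels. Extinction tied to its own room would lower only the concordant-room response and so raise group A's renewal score. The Section C table likewise expects no protection from extinction alone. This stands, and it confines the point mainly to GMA craving and drinking.

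Fifth, the simulation adds nothing to the algebra. That is true; it only puts the identity on the trial's scale.

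Last, Section E says that other control groups were considered and that practical limits decided the choice. Step 6 bears this out: a usefully powered fourth group is out of proportion to a trial of 75. That explains the design but does not extend what it can show.

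**Conclusion.** The point holds as a limit on interpretation. A positive result on both contrasts would show that each component adds benefit in the presence of the other. It could not show whether they interact, because additive and synergistic truths produce the same contrasts, the same similarity of controls and the same chance of success: about 0.62 for beating both at 0.765 SD and 0.40 at 0.61 SD. The identity does not depend on those assumed sizes. The practical weight of the rival rests on the two components having some benefit of their own in daily life, which the documents neither establish nor rule out.

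A reader might infer that the GMA baseline week can stand in for the missing group, for instance by subtracting the changes in A and B from the change in E. It cannot. If c is the soft-drink/soft-drink change and there is no interaction, (c − r − x) − (c − x) − (c − r) = −c. If that unobserved change were a fall of 0.61 SD, the estimate would be +0.61 SD; if a rise of 0.30 SD, −0.30 SD. Nor would a need for both components predict no change in A and B; it predicts that they share the unobserved change. Participants are selected for recent heavy drinking and report on it daily, so zero is not a safe assumption.

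Nothing here weakens the randomised comparisons or the efficacy conclusion.

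**What to change.** In Section E.2, replace the statement that the two controls assess whether both components are required. In Section I.2, add the matching reading of a positive result. Suggested text for both: *adding alcohol retrieval to extinction, and adding extinction to alcohol retrieval, each improved the outcome; whether the components interact is not testable in this design.* Make this conclusion conditional on both pairwise contrasts favouring the experimental group, not on the joint test alone. Keep the I.2 rule for a difference from only one control.

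Add no change-from-baseline contrast as a substitute for the missing group. A fourth group is not requested.

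The cost is a few sentences in the plan and the report, and a weaker mechanistic claim. The sample size, models and efficacy conclusion are unchanged.

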Randomization will be stratified by sex and by the type of alcoholic beverage (beer, wine, or distilled spirits) that will be served in the laboratory sessions, as determined by questionnaire and consultation with the participant, as described below. Blinding is not practical with our manipulations. To reduce expectancy effects, we will not specifically inform participants about the number or nature of the experimental groups; the consent form will make clear that there is at least one control condition but will not be more explicit than that. In the follow-up phone call, after collection of the last outcome measures, we will explain the three-group design of the study and debrief participants about their perceptions of the study. This delay of disclosure will itself be disclosed in the consent form.

Description of laboratory sessions

Overview of laboratory sessions

Sessions will be scheduled to begin at approximately 12:00 pm. Participants will be asked to abstain from drinking alcohol and using any illicit or over-the-counter drugs for at least 24 hours before the session. On arrival at each session, participants will provide a breath sample for measurement of blood alcohol content (BAC) and a urine sample.

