Co-primary outcome 1: Protection from renewal/reinstatement of craving in session 6. We will analyze this in a linear regression model so we can control for a continuous covariate: each participant's mean level of craving in prior sessions (along with any person-level covariates that improve the fit of the model). To test the joint hypothesis that the extinction-retrieval group differs simultaneously from both control groups, we will dummy-code the 3-level predictor Group using two variables: Control Group A (0,1) and Control Group B (0,1), thereby making our intervention group the reference level. We will then perform a Wald test of the joint significance of the two Control Group predictors, maintaining an alpha of .05.

The dependent variable will be operationalized in terms of participants' ratings of alcohol craving in the renewal procedure and the reinstatement procedure from session 6. For each participant, we will generate a summary measure of renewal susceptibility (or, for separate analyses, reinstatement susceptibility) using within-session scores from session 6. For renewal, the score will be calculated as:

(pre-to-post-cue craving change in discordant room) *minus*
 (pre-to-post-cue craving change in concordant room)

For reinstatement, the score will be calculated as:

(pre-to-post-cue craving change after alcohol) *minus*
 (pre-to-post-cue craving change after soft drink)

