Co-primary outcome 2: Reduction of craving and drinking in daily life. This will be analyzed in multilevel models, with the dependent variable operationalized in terms of participants' changes in alcohol craving and alcohol drinking in GMA reports after the four extinction-retrieval sessions, controlling for any preexisting differences. Because we cannot predict the time course of differential changes, our main analyses here will omit GMA data from the period when the four extinction-retrieval sessions are occurring. The dependent variable will be daily frequency of craving reports (or, in a separate analysis, daily number of drinks); the independent variables will be coded the same way as in the models for co-primary outcome 1, with experimental group (3 levels) dummy-coded so the experimental group is the reference level and a Wald test of joint significance can assess whether the experimental group differs simultaneously from both control groups. The continuous covariate will be each participant's overall frequency of craving or drinking during the baseline week of GMA.

Depending on the distribution of the dependent variable, we will use either general linear mixed models (e.g., SAS Proc Mixed) or generalized linear mixed models (e.g., SAS Proc Glimmix or SAS Proc NLMixed)—each of which provides a repeated-measures analysis that can handle missing days or early dropout and can accommodate person-level covariates, which will be included if they improve the fit of the model. These models use maximum-likelihood estimation and allow for specification of an

Abbreviated Title: Lab/GMA drinking

Version Date: 2/16/2022

autoregressive error structure (which can be tested against alternative error structures to provide the best-fitting model). In supplementary analyses, we will examine the time course of any differences that emerge during the period when the four extinction-retrieval sessions are occurring.

Secondary outcomes: Most of the other laboratory measures, such as self-reported craving and drinking at the 30-day follow-up visit, urine biomarkers for drinking, and heart-rate responses to cues, will be analyzed by an ANCOVA approach similar to the one used for the co-primary outcome measure 1. Analysis of the GPS component of the GMA data will be more exploratory, but will include testing for group differences in susceptibility to alcohol craving as a function of nearness to bars and liquor stores—a possible reflection of cue reactivity.

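### Neither co-primary model prespecifies the stratification factors, and both admit covariates by fit, so the stated alpha of .05 may not hold

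*Combined protocol and SAP*

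**What the plan says.** Section E.2 (Experimental groups and randomization): "Randomization will be stratified by sex and by the type of alcoholic beverage". Beverage type has three levels, so there are six strata.

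Section I.2, co-primary outcome 1, is a linear regression with one named covariate, "each participant's mean level of craving in prior sessions", to which the plan adds: "along with any person-level covariates that improve the fit of the model". The test is then fixed: "We will then perform a Wald test of the joint significance of the two Control Group predictors, maintaining an alpha of .05".

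Section I.2, co-primary outcome 2, is a multilevel model whose named covariate is "each participant's overall frequency of craving or drinking during the baseline week of GMA". The plan notes that this model "can accommodate person-level covariates, which will be included if they improve the fit of the model".

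Neither model names sex or beverage type. The plan gives no list of candidate covariates, no measure of fit and no order of selection. It does not say whether group is in the model while covariates are chosen. The sample-size model in section J contains group and a baseline covariate only.

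**The concern.** Two separate mechanisms can move the error rate, in opposite directions.

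- **Strata left out.** Stratified randomisation balances the groups on sex and beverage type. If those factors predict the outcome and are omitted, the model's standard error still contains variation that the design has removed from the comparison. The test becomes conservative and power falls.
- **Covariates chosen by fit.** If covariates are kept because they reduce residual variance in the same data, with group already in the model, the residual error is understated and the group test becomes too liberal.

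The stakes are the decisive tests. Section D treats an effect on the EMA measures alone as enough to show efficacy, and the fit rule governs that model too. Section E.2 says blinding is not practical, and nothing in the plan separates the choice of covariates from knowledge of group.

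**Working it through.** **1. The plan's own power figure.** Inputs from section J: N = 75, f² = .13, 2 group dummies plus 1 baseline covariate, alpha .05. Noncentral F with λ = f² × N = .13 × 75 = 9.75, df1 = 2, df2 = 75 − 3 − 1 = 71. Power = .787, against .80 stated. The smallest f² that gives .80 is .134, which rounds to .13, so the figure is reproduced.

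**2. Cost of adding the strata.** Sex uses 1 df and beverage type 2, so df2 = 75 − 6 − 1 = 68. If they explain nothing, λ is unchanged and power is .786. If they explain a share R² of residual variance, f² becomes .13/(1 − R²):

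| R² | f² | Power |
|---|---|---|
| .10 | .144 | .830 |
| .20 | .163 | .873 |

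The documents give no R². These values are assumptions.

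**3. Simulation of the co-primary 1 model.** There were 10,000 trials per setting (Monte Carlo standard error about .002).

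- From the documents: N = 75, three equal groups, six strata, 25 women and 50 men among completers (section L.3), 2-df joint test.
- Assumed: permuted blocks of 3 within strata; beverage split 50/20/30%; 7 independent null candidates plus the strata. Seven is the number of Session 1 scales after the two beverage questionnaires; 15 is an upper variant. Selection is forward.

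Type I error at nominal .05, 7 candidates:

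| Analysis | R² = 0 | .10 | .20 | .30 |
|---|---|---|---|---|
| Strata always omitted | .045 | .040 | .026 | .015 |
| Strata forced in, no selection | .045 | .054 | .049 | .048 |
| AIC, group in model | .060 | .071 | .066 | .064 |
| Entry at p < .05, group in model | .054 | .062 | .059 | .058 |
| AIC before group is added | .046 | .053 | .050 | .051 |

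Within the same trials, AIC selection with group in the model exceeds the fixed model by 1.6 to 1.7 points (for example .0604 − .0449 = .0155 at R² = 0). With 15 candidates and R² = 0, AIC with group gives .091, p < .05 entry .070, and AIC before group .051. A repeat simulation gave .087 for AIC with 15 candidates, and .039 and .022 for omitted strata at R² = .10 and .20.

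**4. Power at f² = .13.** One group against two equal controls gives f² = d² × 2/9, so d = √(.13 × 9/2) = .765. Section J states a different d for this f². That is a separate matter, and the check here is anchored on f².

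| Analysis | R² = 0 | .10 | .20 |
|---|---|---|---|
| Strata always omitted | .775 | .784 | .799 |
| Strata forced in | .773 | .821 | .869 |
| AIC, group in model | .785 | .825 | .873 |
| AIC before group is added | .750 | .792 | .843 |

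Forced in minus omitted: −.002, .037 and .070. The AIC row with group in the model shows no loss, but it is bought at an inflated alpha. Selection before group is added holds alpha and costs about 2 to 3 points against forcing the strata in (.773 − .750 = .023; .821 − .792 = .029; .869 − .843 = .026).

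**The case against.** The best reply is that the fit rule largely takes care of the strata. Sex and beverage type are person-level variables, so they are eligible, and a fit rule tends to admit prognostic factors. In 3,000 simulated trials per setting under forward AIC, at least one stratum factor entered in about 89%, 99% and 100% of trials at R² = .10, .20 and .30. A reader might infer that the models exclude the strata and that power is therefore lost. The documents do not support that: the factors are unspecified, not excluded. The conservative error and the lost power arise only where the factors are both prognostic and left out.

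The assumed R² may also be generous for co-primary outcome 1. Its score is a difference between two within-person changes in craving, so stable differences between people largely cancel. Sex or beverage type would have to modify renewal or reinstatement itself. That stands, and it is why R² = 0 belongs in the range. For daily number of drinks in co-primary outcome 2, sex is more plausibly prognostic, since the entry thresholds differ by sex, although baseline drinking will absorb part of this.

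The inflation is also conditional. The plan does not say that candidates come from the Session 1 questionnaires, nor that AIC is the criterion, and selecting before group is added holds alpha. A reader might go further and suppose that covariates could be picked to minimise the group p-value, which gave .099 in 2,500 trials at R² = .10. The rule concerns model fit, so that is not what the plan describes.

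What survives is that the plan leaves all of these choices open. It neither guarantees that the strata enter nor restricts selection to a form that holds alpha.

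**Conclusion.** The point holds in this form: the stratification factors are not prespecified, covariates enter by fit, and the stated alpha of .05 may not hold. It does not support saying that alpha fails or that power is lost as a matter of fact.

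For co-primary outcome 1, the plausible excess under AIC selection with group in the model is roughly 1 to 2 points with 7 null candidates and about 4 with 15. There is none if selection precedes group. Omission costs about 4 points of power at R² = .10 and 7 at R² = .20, with type I error of about .04 and .02 to .03, and costs nothing at R² = 0. R², the candidate pool, the beverage split, the block size and the fit criterion are all assumptions. The same rule applies to the multilevel model of co-primary outcome 2, but its effect there was not quantified. This should be corrected before the data are analysed.

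**What to change.** In both co-primary models in section I.2:

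- Name sex and beverage type (three levels) as fixed covariates, with a rule set in advance for pooling beverage categories or strata that turn out sparse.
- Keep one named baseline covariate. For co-primary outcome 2 this is the baseline-week GMA frequency already planned. For co-primary outcome 1 it has to be a craving measure, such as the Session 1 craving rating, because renewal and reinstatement scores do not exist before Session 6.
- Delete the rule admitting covariates by fit from the main analyses. Allow other covariates only in models labelled exploratory.

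The cost is a change of wording and 3 degrees of freedom (residual df 71 to 68 in the linear model). At f² = .13, power moves from .787 to .786 if the factors explain nothing and rises if they explain something. With the strata fixed and no selection, simulated type I error was .045 to .054.
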